- 9. Paired fresh tumor biopsy specimens (to be collected pre- treatment and cycle 3 day 8) will be collected for at least 15 patients (in no certain order) who consent. Subjects with tumor metastases that are not amenable to image guided biopsies or who have a contraindication to biopsy (including but not limited to anticoagulation therapy that cannot be interrupted for a biopsy) are still eligible for participation in the clinical trial without undergoing biopsies. Archival tissue may be used in place of pre-treatment biopsy.

System	Laboratory Value			
Hematological				
Absolute neutrophil count (ANC)	≥1500/µL			
Platelets	≥100 000/µL			
Hemoglobin	\geq 9.0 g/dL or \geq 5.6 mmol/L ^a			
Renal				
Creatinine OR Measured or calculated ^b creatinine clearance (GFR can also be used in place of creatinine or CrCl)	$\leq 1.5 \times \text{ULN } \underline{\text{OR}}$ $\geq 30 \text{ mL/min for participant with creatinine levels}$ $> 1.5 \times \text{institutional ULN}$			
Hepatic				
Total bilirubin	\leq 1.5 ×ULN OR direct bilirubin \leq ULN for participants with total bilirubin levels >1.5 × ULN (patients with clinical evidence of Gilbert's syndrome and elevated bilirubin are eligible for participation).			
AST (SGOT) and ALT (SGPT)	\leq 2.5 × ULN (\leq 5 × ULN for participants with liver metastases)			

Table 2 Adequate Organ Function Laboratory Values

Coagulation					
International normalized ratio (INR) OR prothrombin time (PT) Activated partial thromboplastin time (aPTT)	\leq 1.5 × ULN unless participant is receiving anticoagulant therapy as long as PT or aPTT is within therapeutic range of intended use of anticoagulants				
ALT (SGPT)=alanine aminotransferase (serum glutamic pyruvic transaminase); AST (SGOT)=aspartate aminotransferase (serum glutamic oxaloacetic transaminase); GFR=glomerular filtration rate; ULN=upper limit of normal.					
^a Criteria must be met without erythropoietin dependency and without packed red blood cell (pRBC) transfusion within last 2 weeks.					
^b Creatinine clearance (CrCl) should be calculated per	institutional standard.				
Note: This table includes eligibility-defining laboratory value requirements for treatment; laboratory value requirements should be adapted according to local regulations and guidelines for the administration of specific chemotherapies.					

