- ^a AST/ALT: >3.0 to 5.0 x ULN if baseline normal; >3.0 to 5.0 x baseline, if baseline abnormal; bilirubin:>1.5 to 3.0 x ULN if baseline normal; >1.5 to 3.0 x baseline if baseline abnormal
- ^b AST/ALT: >5.0 to 20.0 x ULN, if baseline normal; >5.0 to 20.0 x baseline, if baseline abnormal; bilirubin:>3.0 to 10.0 x ULN if baseline normal; >3.0 to 10.0 x baseline if baseline abnormal
- c AST/ALT: >20.0 x ULN, if baseline normal; >20.0 x baseline, if baseline abnormal; bilirubin: >10.0 x ULN if baseline normal; >10.0 x baseline if baseline abnormal
- ^d The decision to withhold or permanently discontinue pembrolizumab is at the discretion of the investigator or treating physician. If control achieved or \leq Grade 2, pembrolizumab may be resumed.
- e Events that require discontinuation include, but are not limited to: encephalitis and other clinically important irAEs (e.g., vasculitis and sclerosing cholangitis).

Dose modification and toxicity management of infusion-reactions related to pembrolizumab

Pembrolizumab may cause severe or life-threatening infusion-reactions including severe hypersensitivity or anaphylaxis. Signs and symptoms usually develop during or shortly after drug infusion and generally resolve completely within 24

hours of completion of infusion. Dose modification and toxicity management guidelines on pembrolizumab associated infusion reaction are provided in Table 5.

NCI CTCAE Grade	Treatment	Premedication at Subsequent Dosing
Grade 1	Increase monitoring of vital signs as medically indicated until the	None
Mild reaction; infusion	participant is deemed medically stable in the opinion of the investigator.	
interruption not indicated;		
intervention not indicated		
Grade 2 Requires therapy or influsion	Stop Infusion.	Participant may be premedicated 1.5h (+ 30 minutes) prior to infusion of
interruption but responds	IV fluids	$(\pm 30 \text{ minutes})$ prior to infusion of study intervention with:
promptly to symptomatic	Antihistamines	Diphenhydramine 50 mg po (or
treatment (e.g., antihistamines,	NSAIDs	equivalent dose of antihistamine).
NSAIDs, narcotics, IV fluids);	Acetaminophen	Acetaminophen 500-1000 mg po (or
prophylactic medications	Narcotics	equivalent dose of analgesic).
indicated for ≤ 24 hrs	Increase monitoring of vital signs as medically indicated until the	
	participant is deemed medically stable in the opinion of the investigator.	
	If symptoms resolve within 1 hour of stopping drug infusion, the infusion	

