Based on the known toxicity profiles of pembrolizumab and lenvatinib, certain treatment-related AEs are uniquely associated with one drug versus the other. For example, hypertension, arterial thrombotic events, proteinuria, and hemorrhagic events are known risks for lenvatinib treatment, while immune-related AEs are risks for pembrolizumab treatment. However, certain AEs, such as such as diarrhea, hypothyroidism, and liver enzyme elevation, may be initially considered attributable to either study drug. Therefore, evaluation of attribution is important for determining the study drug most likely related to the AE, or an alternative etiology, and subsequently proper clinical management. The following aspects should be considered:

1. Timing of AE onset

Since lenvatinib is dosed daily and continuously due to a relatively short half-life (28 hours), and pembrolizumab is dosed Q3W due to a long half-life, lenvatinib can be interrupted to assess whether an AE improves/resolves with dechallenge (ie, interruption of treatment) based on the following two scenarios:

- If an AE is identified during a treatment cycle (ie, between 2 pembrolizumab doses), only lenvatinib dose interruption is needed.
- If an AE is identified at the beginning of a treatment cycle, lenvatinib can be interrupted and dosing of pembrolizumab should be held.

If the subject recovers from an AE in response to lenvatinib interruption (ie, positive dechallenge), the event is more likely to be related to lenvatinib. Otherwise, after excluding other alternative explanations, an immune-related AE should be considered.

2. Severity of AE

If an AE is suspected to be treatment related and is severe/life threatening at the time of onset or is rapidly worsened, action including interrupting both drugs and initiating treatment with a corticosteroid (with exception of hypothyroidism, TIDM) and other supportive care should be taken promptly.

- 3. Participants receiving the combination therapy (pembrolizumab + lenvatinib) must discontinue study therapy if any of the following occur:
 - ALT or AST >5 X ULN for more than 2 weeks. Pembrolizumab will have already been permanently discontinued per Table 6,[X], but

Confidential
lenvatinib may be administered at a reduced dose by the time this criterion is met and must be permanently discontinued immediately.

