 ALT or AST >3 X ULN and (TBL >2 X ULN or INR >1.5). Although Table [X] advises pembrolizumab to be withheld (interrupted), and Table [X] advises lenvatinib to have no dose modification or a reduction, if this criterion is met, both drugs must be permanently discontinued immediately.

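### The permanent-stop rules for liver injury misdescribe Table 4 for participants with abnormal baseline values, cite wrong or empty tables, and lack matching scheduled liver and INR tests

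*Combined protocol and SAP*

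**What the plan says.** Item 3 of the overlapping-toxicities text (section 5.2.2 in the contents, just before section 5.2.3) sets two rules for ending therapy in participants on the combination.

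- The first reads "ALT or AST >5 X ULN for more than 2 weeks. Pembrolizumab will have already been permanently discontinued per Table 6,[X". It continues that "lenvatinib may be administered at a reduced dose by the time this criterion is met and must be permanently discontinued immediately".
- The second is "ALT or AST >3 X ULN and (TBL >2 X ULN or INR >1.5". Both drugs must then stop permanently at once. It adds: "Although Table [X] advises pembrolizumab to be withheld (interrupted), and Table [X] advises lenvatinib to have no dose modification or a reduction".

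Table 4 withholds pembrolizumab for Grade 2 AST/ALT or bilirubin elevation and permanently discontinues it for Grade 3 or 4. Its footnotes use multiples of ULN for a normal baseline and multiples of baseline otherwise. Grade 3 AST/ALT, for example, is ">5.0 to 20.0 x baseline, if baseline abnormal", and Grade 2 bilirubin is ">1.5 to 3.0 x baseline if baseline abnormal".

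Table 2 admits AST/ALT up to 2.5 x ULN, with a limit of 5 x "ULN for participants with liver metastases". It admits total bilirubin above 1.5 x ULN when direct bilirubin is not raised, and says that patients with Gilbert's "syndrome and elevated bilirubin are eligible for participation". It waives the INR limit for people on therapeutic anticoagulation.

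Section 5.2.3 asks for liver tests fortnightly through the first two months, then monthly. The Schedule of Activities (section 2.3) marks chemistry at C1D1, C1D15, C2D1 and then Day 1 of each 21-day cycle. It marks INR at screening and C1D1, with later tests only where clinically warranted in people on anticoagulants.

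**The concern.** These are mandatory, permanent stops for suspected liver injury, so the text has to be right about which drug is still being given. The first rule tells staff that pembrolizumab has already ended and names only lenvatinib as the drug left to stop. For a participant who entered with raised enzymes, Table 4 may by then have only withheld pembrolizumab, or may list no action at all.

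A reader who follows the references to check reaches an imaging table or an empty bracket. The second rule does not say whether values that were acceptable at entry count towards it. The scheduled tests do not supply what the rules and section 5.2.3 rely on. Two careful clinicians could therefore disagree on whether a rule is met, or on what has already been stopped.

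**Working it through.** **1. Normal baseline.** Grade 3 begins above 5 x ULN, and Table 4 then permanently discontinues pembrolizumab. Here the plan's statement is true.

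**2. Abnormal baseline.** Let baseline AST/ALT be b x ULN with b > 1. From the Table 4 footnotes, pembrolizumab is withheld above 3b and permanently discontinued above 5b. So:

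- the statement in item 3 is false for values above 5 and up to 5b x ULN, for any b > 1;
- Table 4 lists no AST/ALT action for values above 5 and up to 3b x ULN, a range that exists when b > 5/3 = 1.67.

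| Baseline (x ULN) | Withhold above (3b) | Discontinue above (5b) | Statement false on | No Table 4 action on |
|---|---|---|---|---|
| 2 | 6 | 10 | 5 to 10 | 5 to 6 |
| 2.5 (limit without liver metastases) | 7.5 | 12.5 | 5 to 12.5 | 5 to 7.5 |
| 4 | 12 | 20 | 5 to 20 | 5 to 12 |
| 5 (limit with liver metastases) | 15 | 25 | 5 to 25 | 5 to 15 |

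Example: with b = 2.5, an ALT of 6 x ULN is 6/2.5 = 2.4 times baseline, below Grade 2.

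**3. References.** Table 6 (section 6.1.4.5) covers imaging and treatment after first radiologic progression. The bracketed X is an unfilled template field, not a redaction; similar leftovers stand in section 6.1.2.2 and under Table 6. None of Tables 1 to 10 gives lenvatinib toxicity actions. Section 5.2.3 lists reduced dose levels without a numeric hepatic trigger.

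**4. Second rule against Table 2.** The rule uses ULN multiples and an absolute INR, with no word on baseline.

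- Bilirubin: at a baseline of 2.5 x ULN, Table 4 withholds above 1.5 x 2.5 = 3.75 and discontinues above 3.0 x 2.5 = 7.5 x ULN. Item 3 uses 2 x ULN.
- Eligible example: liver metastases, ALT 4 x ULN, and either an anticoagulated INR of 2 or Gilbert's syndrome with total bilirubin 2.5 x ULN. If pre-existing values count, the rule is met before the first dose.
- INR without anticoagulants: Table 2 allows 1.5 x ULN. The documents give no INR ULN; if it is 1.0, 1.1 or 1.2, the limit is 1.50, 1.65 or 1.80, against an absolute 1.5 in item 3.

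No admitted AST/ALT value meets the first rule at entry, because Table 2 stops at 5 x ULN.

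**5. Schedule.** With 21-day cycles:

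| | Days | Gaps |
|---|---|---|
| Schedule of Activities, chemistry | 1, 15, 22, 43, 64 | 14, 7, 21, 21 |
| Section 5.2.3, fortnightly | 1, 15, 29, 43, 57 | 14, 14, 14, 14 |
| Schedule with C2D15 (day 36) added | 1, 15, 22, 36, 43, 64 | 14, 7, 14, 7, 21 |

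The gap from day 22 to day 43 lies wholly inside the first two months. INR has no scheduled test after C1D1, yet it is one arm of a permanent-stop rule. Appendix 2 lists INR under Chemistry, but it also lists thyroid tests there, and those have their own schedule row, so the grouping does not settle the timing.

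**The case against.** The strongest reply is that the operative instruction is clear. The lead-in to item 3 ends study therapy, and the second rule expressly overrides the dose-modification tables. Table 4 by baseline and item 3 by ULN can coexist as a graded rule with an absolute backstop, which leaves the faulty sentence as explanation only. This stands as far as the final action goes. It does not make the sentence true, and that sentence tells staff what is still being given.

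Other safeguards exist:

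- Items 1 and 2 of the same text hold pembrolizumab for an event found at the start of a cycle, and interrupt both drugs for severe or rapidly worsening suspected treatment-related events.
- The attribution paragraph before Table 4 holds both drugs on Table 4 criteria.
- Table 4 covers immune-related events only; others follow clinical practice.
- Section 5.2.3 says hepatotoxicity may require lenvatinib changes, and it has a Grade 4 rule.
- With three-weekly dosing, normally no more than one pembrolizumab dose falls in a 14-day window.

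These reduce the practical exposure. None supplies a baseline rule, a numeric hepatic trigger for lenvatinib or the missing table.

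The baseline example for the second rule needs several conditions together, and exclusions 12 and 18 narrow the group. That part is closer to a request for clarification.

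On the schedule, section 5.2.3 is worded as a recommendation, while section 6.1 makes the Schedule of Activities binding. By day 57 the difference is four draws against five, and from then on 21-day testing is more frequent than monthly. The mismatch is modest but real. The closer monitoring in Table 4 and the repeat tests in section 6.1.3 follow an abnormal value already seen, and the extra tests in Appendix 2 are discretionary.

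**Conclusion.** The concern holds. The statement that pembrolizumab has already been permanently discontinued is false for any participant with abnormal baseline AST/ALT whose value lies above 5 and up to 5b x ULN. At the entry limits in Table 2, that range reaches 12.5 x ULN, or 25 x ULN with liver metastases. The table references are wrong or empty. The chemistry row departs from section 5.2.3, and INR has no scheduled test behind its arm of the rule.

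The silence on pre-existing values in the second rule is a lesser point, since the documents give no frequency for the combinations that expose it.

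The conclusion assumes that Table 4 is the intended reference; it is the only table with a hepatic rule for pembrolizumab. Because these are permanent-stop rules for liver injury, the text must be corrected.

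**What to change.** Amend the protocol so that Table 2, Table 4 with its footnotes, item 3, section 5.2.3, the Schedule of Activities and Appendix 2 agree:

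- correct the statement that pembrolizumab has already been discontinued;
- state how both item 3 rules apply to abnormal baseline values, Gilbert's syndrome and anticoagulated participants;
- replace the reference to Table 6 and each bracketed X with a real reference, or delete it;
- reconcile the chemistry and INR rows, and the Appendix 2 grouping, with section 5.2.3 and item 3.

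Which thresholds, actions and frequencies apply is for the sponsor's clinicians to decide.

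The cost is amendment wording. If the sponsor changes the schedule rather than section 5.2.3, C2D15 is already a mandatory visit, but adding chemistry there alone still leaves the 21-day gap from day 43 to day 64.

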5.2.3 Monitoring Recommendations on lenvatinib

- BP should be well-controlled prior to the start of lenvatinib. Blood pressure should be monitored after 1 week of treatment with lenvatinib, then every 2 weeks for the first 2 months and monthly thereafter while on treatment. If a patient develops systolic BP ≥140 mmHg or diastolic BP ≥90 mmHg active management is indicated.
- Urine protein should be monitored regularly. If urine dipstick $\geq 2+$ is detected, dose interruptions, adjustments, or discontinuation may be necessary. Discontinue in the event of nephrotic syndrome.
- Monitor and correct all electrolyte abnormalities in all patients.
- Liver function tests should be monitored before initiation of treatment, then every 2 weeks for the first 2 months and monthly thereafter during treatment. In the case of hepatotoxicity, dose interruptions, adjustments, or discontinuation may be necessary.
- Thyroid function, T4 and TSH should be monitored before initiation of, and periodically throughout treatment with lenvatinib. Hypothyroidism should be treated according to standard medical practice to maintain euthyroid state.
- Monitor patients for clinical symptoms or signs of cardiac dysfunction as dose interruptions, adjustments, or discontinuation may be necessary.
- Gastrointestinal toxicity should be actively managed in order to reduce the risk of development of renal impairment or renal failure. Dose interruptions, adjustments, or discontinuation may be necessary.
- Withold lenvatinib for at least 1 week prior to elective surgery. Do not administer for at least 2 weeks following major surgery and until adequate wound healing. The safety of resumption of lenvatinib after resolution of wound healing complications has not been established.
- Events of osteonecrosis of the jaw (ONJ) have been observed with lenvatinib. Invasive dental procedures are an identified risk factor for the development of ONJ. An oral dental examination and appropriate preventive dentistry should be considered prior to initiation of lenvatinib. Patients should be advised regarding periodic dental examinations and oral hygiene practice during lenvatinib therapy. Avoid invasive dental procedures during lenvatinib treatment, if possible. Use caution in patients receiving agents associated with ONJ, such as bisphosphonates and denosumab.

Confidential

• Lenvatinib Dose Reductions/ Interruptions/ Discontinuation:

- Dose reductions of Lenvatinib for treatment related toxicities will proceed as follows:
 - First dose reduction: 14 mg daily
 - Second dose reduction: 10 mg daily
 - Third dose reduction: 8 mg daily
- Discontinuation: lenvatinib should be discontinued in case of life-threatening reactions (e.g., Grade 4) with the exception of laboratory abnormality judged to be nonlife-threatening, in which case they should be managed as severe reactions (e.g., Grade 3).
- Dose interruption: Lenvatinib may be interrupted for situations other than treatment-related AEs such as medical/surgical events and/or unforeseen circumstances not related to study intervention. However, intervention is to be restarted within 2 weeks of treatment hold, unless otherwise discussed with the Sponsor Investigator. The reason for study intervention interruption is to be documented in the patient's study record.

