Hematology		X*	х		х	х		х	x	x	Х	Х	Х	Х			Labs obtained on C1D1 may also be used as the screening value to determine eligibility.
Chemistry		X*	х		х	x		х	х	х	Х	Х	Х	х			*Perform screening laboratory tests within 7 days before the first dose. If performed within 7 days prior to day one CMP does not need to be repeated on Day 1
Thyroid Function Tests (LDH, Free T4, TSH)		X*	x			x			x		x	X		X			Labs obtained on C1D1 may also be used as the screening value to determine eligibility. *Perform screening laboratory tests within 7 days before first dose, then at C2 and every 2 cycles thereafter (C4, C6, etc.) If performed within 7 days prior to day one thyroid function and LDH does not need to be repeated on Day 1

Confidential

Study Period:	Scree	ening		Intervention (21-Day Cycles)				Post t	reatment Visit	S	Notes						
Visit Number/Title: Cycle Day	1/Scro	eening	1	C1 8	15	C	2 15	C3	C4	C5	C6 to C35 1	\geq C36	End of Treatment	Safety Follow- up	Efficacy Follow-up	Survival FU	
Scheduling Window (days)	-42 to - 1	-28 to - 1	±3	±3	±3	±3	±3	±3	±3	±3	±3	±3	At time of treatment discontin uation	Approx. 30d after last dose (± 7d)	Q6W (Y1) or Q9W (Y2+) (± 7d)	Q12W ^a (± 14d)	
Urine Dipstick Testing		X*	x		x	X	x	x	x	X	x	x	х				After C1, collect samples at C1D15 and C2 D15 and up to 3 days before D1 of each cycle. If lenvatinib is discontinued, urine dipstick testing no longer required. Urine dipstick testing (or urinalysis) obtained and reviewed on C1D1 may also be used as the screening value to determine eligibility. If 24-hour urine collection for quantitative assessment of proteinuria is required, C1D1 is postponed to after proteinuria result available. *Perform screening urinalysis tests within 7 days before the first dose. If performed within 7 days prior to day one urine dipstick does not need to be repeated on Day 1

Study Period:	Scree	ening			I	nterve	ntion	(21 - D	ay Cy	cles)	1		Endof	Post tr	eatment Visi	its	Notes
Visit Number/Title: Cycle Day	1/Scre	eening	1	C1 8	15	C	2	C3	C4	C5	C6 to C35 1	≥ C36	Treatment	Safety Follow-up	Efficacy Follow- up	Survival FU	
Scheduling Window (days)	-42 to - 1	-28 to - 1	±3	±3	±3	±3	±3	±3	±3	±3	±3	±3	At time of treatment discontin uation	Approx. 30d after last dose (± 7d)	Q6W (Y1) or Q9W (Y2+) (±7d)	Q12W ^a (± 14d)	

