6.0 TRIAL ASSESSMENTS AND PROCEDURES

6.1 Trial Procedures

- Study procedures and their timing are summarized in the Schedule of Activities (SoA), Section 2.3.
- Adherence to the study design requirements, including those specified in the SoA, is essential and required for study conduct.
- The investigator is responsible for ensuring that procedures are conducted by appropriately qualified (by education, training, and experience) staff.
- All screening evaluations must be completed and reviewed to confirm that potential participants meet all eligibility criteria

- Additional evaluations/testing may be deemed necessary by the investigator, the Sponsor and/or Merck for reasons related to participant safety. In some cases, such evaluation/testing may be potentially sensitive in nature (eg, HIV, Hepatitis C), and thus local regulations may require that additional informed consent be obtained from the participant. In these cases, such evaluations/testing will be performed in accordance with those regulations.
- Procedures conducted as part of the participant's routine clinical management (eg, blood count) and obtained before signing of ICF may be utilized for screening or baseline purposes provided the procedure met the protocol-specified criteria and were performed within the time frame defined in the SoA.
- All screening evaluations must be completed and reviewed to confirm that potential participants meet all eligibility criteria. The investigator will maintain a screening log to record details of all participants screened and to confirm eligibility or record reasons for screening failure, as applicable.

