6.1.3 Clinical Safety Laboratory Assessments

Refer to Appendix 2 for the list of clinical laboratory tests to be performed and to the SoA for the timing and frequency.

• The investigator or medically qualified designee (consistent with local requirements) must review the laboratory report, document this review, and record any clinically relevant changes occurring during the study in the AE section of the CRF. The laboratory reports must be filed

with the source documents. Clinically significant abnormal laboratory findings are those which are not associated with the underlying disease, unless judged by the investigator to be more severe than expected for the participant's condition.

- All protocol-required laboratory assessments, as defined in Appendix 2, must be conducted in accordance with the laboratory manual and the SoA.
- If laboratory values from non-protocol-specified laboratory assessments performed at the institution's local laboratory require a change in study participant management or are considered clinically significant by the investigator (e.g., SAE or AE or dose modification), then the results must be recorded in the appropriate CRF (e.g., SLAB).
- For any laboratory tests with values considered clinically significantly abnormal during participation in the study or within 30 days after the last dose of study intervention, every attempt should be made to perform repeat assessments until the values return to normal or baseline or if a new baseline is established as determined by the investigator.

Details regarding specific laboratory procedures/assessments to be performed in this study are provided below. The total amount of blood/tissue to be drawn/collected over the course of the study (from prestudy to poststudy visits), including approximate blood/tissue volumes drawn/collected by visit and by sample type per participant can be found in the Lab Manual. Refer to the SoA (Section 2.3) for the timing of laboratory assessments.

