Appendix 2: Clinical Laboratory Tests

- The tests detailed in Table 9 will be performed by the local laboratory.
- Protocol-specific requirements for inclusion or exclusion of participants are detailed in Section 5.1 of the protocol.
- Additional tests may be performed at any time during the study as determined necessary by the investigator or required by local regulations.

Laboratory	Parameters						
Assessments					-		
Hematology	Platelet Count		RBC Indices:		WBC count with		
	RBC Count		MCV		Differential:		
	Hemoglobin				Neutrophils		
	Hematocrit			Lymphc		hocytes	
				Monocytes			
				Eosinophils			
				Basophils			
Chemistry	BUN	Potass	ium	AST/SGOT		Total bilirubin (and	
						direct bilirubin, if	
						total bilirubin is	
						elevated above the	
						ULN)	
	Albumin	Bicarbonate		Chloride		Phosphorous	
	Creatinine		n	ALT (including LFT)/SGPT		Total Protein	
	Glucose [Indicate if	Calcium		Alkaline		Thyroid Funtion	
	fasting, or			phosphatase		Tests (LDH, Free	
	nonfasting]					T4, TSH)	
	INR or PT and						
	aPTT						
Routine	Specific gravity						
Urinalysis	• Specific gravity						
	• pH, glucose, protein, blood, ketones, nitrite, leukocyte esterase by dipstick						
	Microscopic examination (if blood or protein is abnormal)						
	• 24-hour urine collection for quantitative assessment of proteinuria may also be required						
	at screening to determine eligibility						
Pregnancy	Highly sensitive serum hCG pregnancy test (as needed for WOCBP)						
Testing							
Other Screening	• FSH (as needed in WOCBP only)						
Tests							
ALT=alanine aminot	ransferase; AST=aspartate	aminotra	ansferase; BUN=b	olood urea nitroger	n; FSH=f	follicle-stimulating	
hormone; hCG=human chorionic gonadotropin; MCH=mean corpuscular hemoglobin; MCV=mean corpuscular volume;							
RBC=red blood cell; SGOT=serum glutamic-oxaloacetic transaminase; SGPT=serum glutamic-pyruvic transaminase;							
ULN=upper limit of normal; WOCBP=women of childbearing potential; WONCBP=women of nonchildbearing potential							

Table 9 Protocol-required Safety Laboratory Assessments

The investigator (or medically qualified designee) must document their review of each laboratory safety report.

Protocol 2021000802 MISP 60931 Version Date: 30Jul2024

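### Section 5.2.3 asks for two-weekly liver tests over the first 2 months and a week-1 BP; the Schedule of Activities leaves two 21-day chemistry gaps and no on-treatment BP before day 15

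*Combined protocol and SAP*

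**What the plan says.** **Section 5.2.3 (monitoring on lenvatinib).** For the liver: "Liver function tests should be monitored before initiation of treatment, then every 2 weeks for the first 2 months and monthly thereafter during treatment". For BP: "Blood pressure should be monitored after 1 week of treatment with lenvatinib", then every 2 weeks for 2 months and monthly after that. At a systolic value of 140 mmHg or a diastolic value of 90 mmHg, "active management is indicated".

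**Section 2.3 (SoA).**
- The Chemistry row is marked at C1D1, C1D15, C2D1, C3D1, C4D1 and day 1 of later cycles. It is blank at C2D15. Its note allows recent screening values to stand in for day 1 ("CMP does not need to be repeated on Day 1") and adds nothing for C2D15.
- The Vital Signs row is marked at C1D1, C1D15, C2D1, C2D15 and day 1 of later cycles. It is blank at C1D8. Its note makes the day 15 visit compulsory in cycles 1 and 2, and optional from cycle 3 if BP needs watching.
- C1D8 carries only a contact to assess early toxicity. An unscheduled visit before C1D15 is possible if safety requires it.

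**Appendix 2.** The chemistry panel holds AST, bilirubin and "ALT (including LFT)/SGPT".

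**Status of the SoA.** Section 6.1: "Adherence to the study design requirements, including those specified in the SoA, is essential and required for study conduct". Section 6.1.3 says protocol-required laboratory assessments "must be conducted in accordance with the laboratory manual and the SoA".

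**The concern.** The protocol sets its own early monitoring standard in one section and does not schedule it in the section that staff use to book visits. C2D15 is already compulsory, with vital signs and a urine dipstick, yet no liver test is drawn there.

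Three things are at stake.
- **Liver.** Participants with liver metastases may enter with AST or ALT up to 5 x ULN (Section 5.1.1, Table 2), and Section 5.2.2 names liver enzyme elevation as an event that either drug could cause. Its permanent-stop rule for transaminases above 3 x ULN with raised bilirubin or INR can be triggered only once someone has drawn the blood.
- **Attribution.** Section 5.2.2 treats an event found between pembrolizumab doses differently (interrupt lenvatinib only) from one found at the start of a cycle (also hold pembrolizumab). Cycle 2 has no scheduled mid-cycle liver test on which to use that distinction.
- **Blood pressure.** Section 5.2.2 lists hypertension as a known lenvatinib risk. The 140/90 rule cannot be applied at week 1 without a reading, and a toxicity contact without a measurement will not find symptomless hypertension.

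**Working it through.** The plan gives no figure for this point, so there is none to reproduce. The check maps the SoA marks to study days and compares the gaps with Section 5.2.3.

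**Is the blank cell real?** The urine dipstick row is marked in both day 15 columns, and its note says "collect samples at C1D15 and C2 D15". In the same column layout, the Chemistry cell at C2D15 is empty. This is not a table-reading artefact.

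**Study days.** With 21-day cycles: C1D1 = 1, C1D8 = 8, C1D15 = 15, C2D1 = 22, C2D15 = 36, C3D1 = 43, C3D15 = 57, C4D1 = 64. Two-weekly liver testing implies days 15, 29, 43 and 57.

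| Check | Scheduled days | Gaps (days) |
|---|---|---|
| Chemistry now | 1, 15, 22, 43, 64 | 14, 7, 21, 21 |
| Chemistry with C2D15 | 1, 15, 22, 36, 43, 64 | 14, 7, 14, 7, 21 |
| Chemistry with C2D15 and C3D15 | 1, 15, 22, 36, 43, 57, 64 | 14, 7, 14, 7, 14, 7 |
| BP now | 1, 15, 22, 36, 43, 64 | 14, 7, 14, 7, 21 |
| BP with C1D8 | 1, 8, 15, 22, 36, 43, 64 | 7, 7, 7, 14, 7, 21 |

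With the +/-3-day windows, each 21-day gap can run from 21 - 6 = 15 to 21 + 6 = 27 days.

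**Mean delay to the next liver test.** The documents give no onset timing, so uniform onset is assumed. An onset falls in a gap of length g with probability proportional to g and then waits g/2 on average, so mean delay = sum(g^2) / (2 x sum(g)).
- Onset over days 1-64: now (196 + 49 + 441 + 441)/126 = 1127/126 = 8.94 days. With C2D15: (196 + 49 + 196 + 49 + 441)/126 = 931/126 = 7.39 days. Saving 1.56 days.
- Onset over days 1-43: 686/84 = 8.17 to 490/84 = 5.83 days. Saving 2.33 days.
- Onset over days 22-43 only: 441/42 = 10.5 to 245/42 = 5.83 days. Saving 4.67 days. This is the most favourable case, because it restricts onset to the gap being repaired.
- Adding C3D15 as well, onset over days 1-64: (3 x 196 + 3 x 49)/126 = 735/126 = 5.83 days. Saving 8.94 - 5.83 = 3.11 days.

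**Long delays.** In each 21-day gap, an onset in the first 21 - 14 = 7 days waits more than 14 days for the next scheduled test, which is one third of that gap. Over days 1-64 this is 14 of 63 days now, 7 of 63 with C2D15, and 0 of 63 with C3D15 too, all at nominal visit days. With windows, C2D1 to C2D15 can itself run from 14 - 6 = 8 to 14 + 6 = 20 days.

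**BP.** First scheduled on-treatment reading: day 15, or 12-18 with the window. For uniform onset over days 1-15, mean delay is 14^2/28 = 7.0 days now and (7^2 + 7^2)/28 = 3.5 days with a C1D8 reading. The longest interval falls from 14 to 7 days.

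**The case against.** **Safeguards exist.** Additional tests may be done at any time, C1D8 can lead to an unscheduled visit, adverse events are reviewed weekly (Section 8.7), and exclusion 16 removes BP that is uncontrolled at entry. These lower the risk. But extra tests and visits need a reason to act, weekly review produces no laboratory value, and exclusion 16 concerns BP before lenvatinib. None of them schedules either check.

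**The gain is small.** This stands. The main estimate is 1.6 days on an assumed onset pattern, and the 4.7-day figure should not be quoted alone.

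**Marking C2D15 does not fully align the two sections.** This also stands. Days 43-64 form an identical 21-day liver-test gap, largely inside the first 2 months, and BP at C3D15 is optional. It would be wrong to call the rest of the early schedule adequate.

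A reader might infer more than the documents support in three ways:
- *That the SoA overrides Section 5.2.3, so a site missing both checks is fully compliant.* Section 6.1 requires the design requirements including those in the SoA; it does not make the SoA exclusive or rank it above Section 5.2.3. That section is headed as recommendations, but it is still protocol text, and the laboratory manual is not among the documents. What can be said is that the sections disagree.
- *That the gaps defeat the stop rule for transaminases above 5 x ULN lasting beyond 2 weeks.* That rule concerns an elevation already being managed, with pembrolizumab already stopped; Table 4 by then suggests weekly or more frequent liver tests. The routine interval bears on first detection.
- *That a C2D15 draw rules out any wait over 14 days in cycle 2.* That holds only at nominal visit days. Nor would the draw clearly supply INR, which has its own SoA row marked only at screening and C1D1.

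**Conclusion.** The point holds as an inconsistency between two protocol sections with a safety consequence. Liver chemistry has two 21-day gaps where Section 5.2.3 asks for 14 days, and the first on-treatment BP comes about a week later than that section asks. After month 2 there is no problem: 3-weekly checks exceed the monthly standard.

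The effect is later first detection of a liver enzyme rise or hypertension, not failure to follow a known event. Its average size is modest and depends on the uniform-onset assumption. The gap lengths follow from the SoA and 21-day cycles alone. The point does not touch the primary endpoint, sample size, power table or interim rule. The change should be made because it is cheap and meets the protocol's own stated standard.

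**What to change.** 1. Mark Chemistry at C2D15 in the SoA. Cost: one blood draw per participant at an existing mandatory visit.
2. Add a BP reading to the C1D8 contact, in clinic or by home cuff reported at the contact, so that the 140/90 rule can be applied at week 1. Cost: one reading per participant, needing a cuff or a short visit because C1D8 is only a contact.
3. State openly that cycle 3 has the same liver-test gap and only an optional day 15 BP. Draw liver tests whenever a participant attends C3D15. Then choose one: schedule C3D15 for everyone, which adds a visit and brings the longest nominal gap through day 64 to 14 days for both checks; or amend Section 5.2.3 to say that 3-weekly testing is accepted from C3, which costs only a text change.

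For 30 participants, steps 1 and 2 amount to at most 30 draws and 30 readings.
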